### Biofeedback Set-Up:

- Each limb placed on separate portable force plates
- Biofeedback viewed on 32" screen at eye level that is 200 cm from the front of force plates and 130 cm from the ground to the bottom edge of the screen
  - During rehab feet will be placed near anterior portion of plate even with tape. Otherwise, no positioning is cued

### Biofeedback Conditions:

- Ground reaction force (GRF) only
  - Top row
  - Verbal Instructions: "Your goal is to keep the green/blue bar as close to the vertical line in the middle of the screen as possible. As you shift to the left the bar will shift left with you and eventually turn red. As you shift to the right the bar will shift right with you and eventually turn red. If the bar isn't visible, it means your weight is evenly distributed side to side. You will be performing \_\_\_\_ squats with your arms \_\_\_\_\_. I will give you a countdown to begin your squats. The countdown will be '3,2,1,Go' and we want you to begin on 'Go.' Again the goal is to keep the green/blue bar as close to the vertical line in the middle of the screen as possible."
- Center of pressure (COP) only
  - Middle row
  - Verbal Instructions: "Your goal is to keep the green/blue line level and even with the dotted line in the middle of the screen. If you put weight through your left heel and right toe the line will tilt and eventually turn red. If you put weight through your right heel and left toe the line will also tilt and eventually turn red. You will be performing \_\_\_\_ squats with your arms \_\_\_\_\_. I will give you a countdown to begin your squats. The countdown will be '3,2,1,Go' and we want you to begin on 'Go.' Again the goal is to keep the green/blue line as level as possible and even with the dotted line in the middle of the screen."
- GRF + COP
  - Bottom Row
  - Verbal Instructions: "This will be a combination of the two versions you've previously done. Your goal is to keep the green/blue bar as close to the vertical line in the middle of the screen as possible and to keep the green/blue line level and even with the dotted line in the middle of the screen. As you shift to the left the bar will shift left with you and eventually turn red. As you shift to the right the bar will shift right with you and eventually turn red. If the bar isn't visible, it means your weight is evenly distributed side to side. Now, if you put weight through your left heel and right toe the line will tilt and eventually turn red. If you put weight through your right heel and left toe the line will also tilt and eventually turn red. Your goals are to keep both the bar and the line green/blue. You will be performing \_\_\_\_ squats with your arms \_\_\_\_\_. I will give you a countdown to begin your squats. The countdown will be '3,2,1,Go' and we want you to begin on 'Go.' Again the goal is to keep the green/blue bar as close to the vertical line in the

middle of the screen as possible and the green/blue line as level as possible and even with the dotted line in the middle of the screen.”

- Control Cues
  - “I’d like you to squat with your arms \_\_\_\_, keeping your knees in line with your toes, hips back, and weight evenly balanced between your feet. I will give you a countdown to begin your squats. The countdown will be ‘3,2,1,Go’ and we want you to begin on ‘Go.’”

Bodyweight Squat Protocol Modifications	
Factor	Rehab Modification
>50% weightbearing restriction (e.g. due to complex concomitant meniscal repair)	
 
Complete baseline study testing and initiate bodyweight squat protocol when 50% weightbearing is allowed (e.g. at 4 weeks or 6 weeks after ACLR)
 
Full 8 weeks of squat protocol is still completed
 
Delay post-intervention testing (e.g. if squat protocol is initiated at 4 weeks post-ACLR, complete post-intervention testing at 12 weeks post-ACLR instead of 10 weeks post-ACLR)
 

<90° knee flexion ROM restrictions	
 
Complete squat protocol within ROM restrictions (e.g. only squat to 60° until greater knee flexion ROM allowed)
 

< 16 visits completed within squat protocol	
 
Include participant data if at least 8/16 visits are completed during the 8 week squat protocol
 

**Bodyweight Squat Protocol – Documentation (to be transitioned to electronic REDCap format):**

**Squat Protocol Week:** \_\_\_\_\_

**Date:** \_\_\_\_\_

**Location of Squat Training:**  Isolated quiet room  Shared exercise space

**Timing of Squat Training:**  Before strengthening exercises  After strengthening exercises

**Squat Depth (knee flexion):**  30°  40°  50°  60°  70°  80°  90°

Rest: _____	REPS			ARMS	Condition	ACCURACY	
	5	8	10			%	N/A
Set 1	—	—	—	—	—	—	—
Set 2	—	—	—	—	—	—	—
Set 3	—	—	—	—	—	—	—
Set 4	—	—	—	—	—	—	—
Set 5	—	—	—	—	—	—	—
Set 6	—	—	—	—	—	—	—

**Cuing**

- During the squat protocol
  - Treatment group will receive externally focused cues for all activities during the period they are receiving the squat protocol
  - Control group will receive internally focused cues for all activities during the period they are receiving the squat protocol
- After the squat protocol is completed
  - Both groups can receive a hybrid approach to cuing based on what each individual person responds best to with regard to form correction
- Examples

- Internal cues
  - Knees in line with toes
  - Don't let knees touch
  - Push down with heel
- External cues
  - Keep knee pointed at this object
  - Don't let your leg hit this object

## Statistical Analysis Plan

### **Data analysis plan:**

A p-value less than 0.05 will be considered statistically significant unless otherwise specified.

To determine the efficacy of the visual biofeedback program, analyses of covariance (ANCOVA) will be used at 3 and 6 months after ACLR to test differences in the interlimb ratio (ILR = injured limb / uninjured limb) of the knee flexion moment impulse during squatting, after adjusting for baseline knee flexion moment impulse. An ANCOVA will also be used to test differences in the ILR of the vertical ground reaction force impulse.

Independent t-tests will be used to test the percent change in cartilage T2 relaxation time in the injured knee from 2 weeks to 6 months after ACLR between groups, quadriceps strength, and gait biomechanics. For quadriceps strength, limb symmetry indexes will be computed (LSI = injured limb / uninjured limb x 100%).

If assumptions for any of these tests are violated, a nonparametric test will be conducted.

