**Sample Size and Randomization**

1. N=34 (17 in squat biofeedback group and 17 in control group)
  - a. Target equal number of women and men

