### **Sample size analysis:**

Using our preliminary data, a sample size of 20 (10 per group) achieves 82.5% power to detect a difference in the knee flexion moment (KFM) impulse ILR of 0.283 during squats between the biofeedback (expected ILR=0.800±0.183) and standard of care group ( expected ILR=0.517±0.228) using a two-sided hypothesis test and p-value of 0.05. Group differences are based on our preliminary data after standard of care: KFM impulse ILR at 4 months (N=20): 0.517±0.228; KFM impulse ILR at 10 months (N=5): 0.971±0.183. Thus, our expected KFM impulse ILR for the biofeedback group at 3 and 6 months is 0.800±0.183. To test our hypothesis that the biofeedback group will walk with a greater KFM than the standard of care group, the minimal detectable change (MDC) of 0.09 N·m/kg·m with a standard deviation of 0.08 was used (Gardinier 2013). Using this expected group difference, a sample size of 28 (14 per group) achieves 81.7% power using a two-sized hypothesis test and p-value of 0.05. To account for 10% attrition, 32 participants will be enrolled.

A sample size of 30 (15 per group) achieves 81.0% power to detect a group difference of  $2.9 \pm 2.7$  milliseconds in T2 relaxation time (primary outcome; measured from 2 weeks to 6 months in the injured knee). This expected group difference is based on a change in T2 relaxation time of  $2.9 \pm 2.7$  milliseconds in the medial femoral cartilage by 6 months after ACLR as reported by Kumar et al. Preliminary data of 37 participants from our ongoing NIH R21 study indicate that quadriceps strength LSI following standard care is  $66.0 \pm 21.1\%$  at 6 months after ACLR. The evidence-based clinical targets for quadriceps strength at 6 months is 90.0%. Using the expected quadriceps strength LSI of 66.0% in the control group and 90.0% in the intervention group at 6 months after ACLR with a pooled standard deviation of 21.1%, a sample size of 30 (15 per group) achieves 91.8% power using a two-sided hypothesis. To account for attrition, 34 participants will be enrolled.

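### The T2 outcome labelled primary is powered in milliseconds but tested as percent change with no cartilage region named, and the analysis plan does not say that it decides efficacy

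*Combined protocol and SAP*

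**What the plan says.** **Sample size analysis.** One outcome is labelled primary: "primary outcome; measured from 2 weeks to 6 months in the injured knee". Its power statement begins "A sample size of 30 (15 per group) achieves 81.0% power to detect a group difference of" and continues with 2.9 ± 2.7 milliseconds. The same paragraph explains that this figure is a change reported in medial femoral cartilage by 6 months after reconstruction. The paragraph ends "To account for attrition, 34 participants will be enrolled". The Sample Size and Randomization section agrees: "N=34 (17 in squat biofeedback group and 17 in control group". The preceding paragraph, on squat and walking KFM, arrives at 32.

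**Data analysis plan.** No outcome is called primary. The section opens "To determine the efficacy of the visual biofeedback program, analyses of covariance (ANCOVA) will be used at 3 and 6 months after ACLR", and the outcome of those ANCOVAs is the interlimb ratio (ILR) of KFM impulse during squatting. An ANCOVA of the vertical ground reaction force (vGRF) impulse ratio follows. T2 comes in the next paragraph, in one sentence with quadriceps strength and gait, where independent t-tests are to "test the percent change in cartilage T2 relaxation time in the injured knee from 2 weeks to 6 months". No cartilage region is given. The general rule on significance is "A p-value less than 0.05 will be considered statistically significant unless otherwise specified", and nothing else is specified for any of these tests.

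**The concern.** There are two gaps between adjoining sections of the same plan.

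- **Scale and region.** Power is stated for an absolute difference in milliseconds, using a figure from one cartilage region. The planned test uses change divided by each participant's own baseline, in a region left open. The SD of a percent change depends on the level and spread of baseline T2 and on how change relates to baseline, so the 81.0% does not carry over automatically. If several regions are measured, an unnamed region also leaves open which result is the primary one.
- **Which result decides.** The primary label stands in a parenthesis in a power sentence. The section that governs the analysis does not repeat it, and uses its only efficacy wording for a different outcome at two visits. A report could follow either section.

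At stake are the stated power of the primary test and a clear rule, fixed before results are known, for which result supports a claim of efficacy.

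**Working it through.** **1. Reproduce the stated power.** Inputs from the sample size section: n = 15 per group, difference 2.9 ms, SD 2.7 ms. The significance level of 0.05 is from the data analysis plan. The T2 sentence does not state sidedness.

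- Standardised difference: 2.9 / 2.7 = 1.074.
- Noncentrality: 2.9 / (2.7 × √(2/15)) = 2.941, with 28 degrees of freedom and two-sided critical value 2.048.
- Power from the noncentral t distribution: 81.04%, against 81.0% stated.
- Alternatives: a one-sided t-test gives 89.0% and a two-sided normal approximation 83.7%. Neither matches.

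The stated figure is therefore for a two-sided t-test on absolute milliseconds.

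**2. Reproduce the enrolment.** 30 / (1 − 0.10) = 33.3, rounded up to 34. The 10% is stated for the figure of 32 and is not repeated for 34, but it reproduces the number.

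**3. Set the two descriptions side by side.**

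| Item | Sample size analysis | Data analysis plan |
|---|---|---|
| Status of T2 | Primary | Not labelled |
| Knee and interval | Injured, 2 weeks to 6 months | The same |
| Scale | Milliseconds | Percent change |
| Region | Source figure is medial femoral cartilage | None named |
| Efficacy wording | None | Squat KFM impulse ratio, 3 and 6 months |

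**4. Power on the planned scale.** This cannot be derived from the documents, because they give no baseline T2 and no SD of percent change. The following is an illustration under assumptions.

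- *Taken from the plan:* 15 per group; SD of change 2.7 ms; mean change 2.9 ms in one group and 0 in the other.
- *Assumed:* baseline mean 35 to 45 ms, baseline SD 2 to 6 ms, normal distributions, and a within-group correlation between baseline and change of 0 or −0.5.
- *Formula:* percent change = 100 × change / baseline. At the mean baseline, 2.9 ms is 2.9/35 = 8.3%, 2.9/40 = 7.25% or 2.9/45 = 6.4%.
- *Method:* simulated trials, two-sided t-test at 0.05.

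| Assumed baseline-change correlation | Power on percent change |
|---|---|
| 0 | about 79% to 81% |
| −0.5 | about 74% to 80% |

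The lowest value comes from the smallest mean with the largest spread (35 ms, SD 6 ms) and correlation −0.5. With a baseline SD of 2 ms, power stays at about 80% or 81% in every case.

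**The case against.** The strongest reply is that the hierarchy is already settled. The two sections adjoin within one plan and exactly one outcome is labelled primary. The analysis plan does test it, in the same knee, over the same interval and by a named test. Enrolment follows the T2 and strength paragraph (34) rather than the KFM paragraph (32). The efficacy phrase opens the section and sets no decision rule. Most of this stands, so the hierarchy part is an ambiguity to remove rather than a contradiction between two primary outcomes.

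Three stronger readings are tempting, and the documents do not support them.

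- **KFM is a competing primary outcome, so type I error is inflated.** Nothing labels KFM primary, and no section says that a significant result at either KFM visit is enough. If the T2 label binds, the primary test is a single test at 5%.
- **The primary outcome has been left out of the analysis.** It has not. Its label, its region and the scale used for its power are what is missing there.
- **The change of scale leaves the trial badly underpowered.** A large loss appears only if a much smaller standardised difference is simply assumed. When percent change is built from the plan's own millisecond figures, the loss is between almost nothing and about 7 points under the assumptions used here.

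It can also be said that choosing milliseconds is partly a preference, since restating the power for percent change would close the gap as well. That is fair, and the fix allows it. What the reply does not answer is that the 81.0% belongs to a test other than the planned one, and that the region of the primary test is open.

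**Conclusion.** The point holds as a mismatch of scale and region for the labelled primary outcome, together with an ambiguity over which result decides efficacy. The plan's arithmetic is sound: 81.0% and 34 both reproduce. The planned percent-change test has no stated power. Under the assumed baselines its power is about 74% to 81%, so the loss is probably small to moderate. That range rests on assumed baseline means, SDs and correlations, none of which the documents give, and on treating the powered SD as the SD of change in both groups. The mismatch itself needs no assumption, as it can be read directly from the two sections. It should be corrected before results are known, but it does not show that the sample size is wrong.

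**What to change.** In the data analysis plan:

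1. Name one primary outcome: T2 change in milliseconds in the injured knee from 2 weeks to 6 months, tested at two-sided 0.05. Name one region, either medial femoral cartilage, to match the power calculation, or another single region with the power restated for it.
2. Report percent change as supportive. If it is to remain the primary scale, restate the power on that scale with a sourced SD.
3. Reword the efficacy sentence, and label the KFM impulse ratio (3 and 6 months), the vGRF impulse ratio, quadriceps strength and gait as secondary, so that none of them alone supports an efficacy claim.
4. If the sponsor in fact intends KFM as primary, name one visit and remove the primary label from T2.

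**Cost.** With milliseconds and medial femoral cartilage this is a text edit: enrolment stays at 34 and power at 81.0% with 15 per group after attrition. Keeping percent change or choosing another region requires a new power statement with figures the documents do not give, and 34 can be called adequate only after that. The downside is that KFM loses its standing as a basis for claiming efficacy by itself.

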**Volitional Isometric & Isokinetic Quadriceps Strength Testing (Biologix) (3, 6 months):**

Equipment: Biologix (C-MOVA)

Set-Up:

- a. Use participant weight measured in lab
- b. Before participant is ready to test (while performing other testing)
  - i. Power on machine: turn on black button then computer
  - ii. Open Biologix
  - iii. Go to patient → if new patient go to add patient → enter patient information (Last name, first name, gender, involved limb, weight (kg), enter RTS under ID #)
  - iv. If returning patient, click open and select patient → select the last testing session → select repeat and same protocol will automatically be applied
  - v. Click save
- a. Click protocol → click Linked → Select RTS Testing or RTS Testing plus 180 per sec depending on time point.
  - 1. ISOM: UNI: AWAY: TEST: 90, 90, 90 (RTS Isometric: KNEE: EXT/FLX **(3, 6 months)**)
  - 2. ISOK: UNI: CON/CON: TEST: 60/60 (RTS Isokinetic): KNEE: EXT/FLX **(3, 6 months)**
  - 3. ISOK: UNI: CON/CON: TEST: 180/180 (RTS Isokinetic): KNEE: EXT/FLX **(6 months)**
  - 4. ISOM: UNI: AWAY: TEST: 90, 90, 90 (RTS Isometric: KNEE: EXT/FLX **(3, 6 months)**)
  - 5. ISOK: UNI: CON/CON: TEST: 60/60 (RTS Isokinetic): KNEE: EXT/FLX **(3, 6 months)**
  - 6. ISOK: UNI: CON/CON: TEST: 180/180 (RTS Isokinetic): KNEE: EXT/FLX **(6 months)**
- c. Set up chair positioning (will test uninvolved limb first) (if 6-month testing then set up according to 3-month testing position)
  - i. Seat A/P forward/backward position
  - ii. Seat height
  - iii. Seat depth
  - iv. Attachment Arm length
  - v. Dynamometer distance left/right
  - vi. Set-up guidelines:
    - a. Secure thigh, chest, and waist straps
    - b. Top of dynamometer cuff just proximal to talocrural joint (2 finger widths above medial malleolus)
    - c. Knee joint center should be in line with arm of rotation of dynamometer
- e. After subject is set-up, complete testing:
  - i. Select side

- ii. Set away limit
- iii. Set toward limit
- iv. For calibrate position: use level to calibrate arm at 90 degrees
- v. For limb weight put limb to end extension ROM and lock in that position and ask subject to relax
- vi. Select continue
- vii. Select start
- viii. Isometric: Begin trial reps
  - 1. Have subject cross arms over chest when ready to contract
  - 2. Practice trials at 50%, 75%, and 100% of maximum effort completed to assure no pain or discomfort present.

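### Squat efficacy is tested at two visits and on two ratios, each at 0.05, with no deciding test, and the analysis plan gives no special role to the labelled primary outcome, T2

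*Combined protocol and SAP*

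**What the plan says.** Under "Data analysis plan" in the Statistical Analysis Plan:

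- One significance level covers everything: "A p-value less than 0.05 will be considered statistically significant unless otherwise specified". Neither that section nor "Sample size analysis" specifies another level for any test.
- The efficacy question goes to the squat ANCOVAs. The sentence opens by giving the determination of efficacy as its purpose, and says that "analyses of covariance (ANCOVA) will be used at 3 and 6 months after ACLR to test differences in the interlimb ratio". The outcome is the injured-to-uninjured ratio (ILR) of the KFM impulse, adjusted for baseline.
- A second squat ratio follows, without a visit: "An ANCOVA will also be used to test differences in the ILR of the vertical ground reaction force impulse".
- A separate paragraph, which does not use the word efficacy, covers the rest: "Independent t-tests will be used to test the percent change in cartilage T2 relaxation time in the injured knee from 2 weeks to 6 months", together with quadriceps strength and gait biomechanics.

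Under "Sample size analysis", the primary label appears once, in a parenthesis: "T2 relaxation time (primary outcome; measured from 2 weeks to 6 months in the injured knee". The same section powers the KFM ratio "using a two-sided hypothesis test and p-value of 0.05".

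No passage names a deciding visit or squat ratio, sets an order of testing, adjusts for multiplicity, or says how a result at one visit only is to be read.

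**The concern.** The section that defines the analysis determines efficacy from at least three squat tests, each at 0.05. A difference at 3 months but not at 6, or on vGRF but not on KFM, could be reported as efficacy at p<0.05, and nothing in the plan stops that. The 5% level then describes each test and not the efficacy claim.

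The two sections also point to different outcomes. A reader of the sample size text would take T2 as the outcome that decides the trial. A reader of the analysis text would take the squat ratios, with T2 listed beside strength and gait. If T2 and the squat ratios disagree, the plan does not say which result answers the trial's question.

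**Working it through.** **Inputs from the documents.** Two-sided 0.05 per test. KFM impulse ILR expected at 0.800 (SD 0.183) with biofeedback and 0.517 (SD 0.228) with standard care, difference 0.283, stated power 82.5% at 10 per group. T2 difference 2.9 ms, SD 2.7 ms, stated power 81.0% at 15 per group. Enrolment is 17 per group; 15 per group is the number the plan uses for its T2 and strength calculations.

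**Assumptions.** The documents give no correlation between the squat tests, so a common value from 0 to 0.9 is used. The vGRF ANCOVA counts as one test if read literally, and as two if it follows the 3- and 6-month pattern.

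**Step 1: reproduce the plan's power.** Pooled SD = √[(0.183² + 0.228²)/2] = 0.2067. Standardised difference = 0.283/0.2067 = 1.369. With 10 per group the noncentrality is 1.369/√(2/10) = 3.06 on 18 degrees of freedom, and a two-sided t-test at 0.05 has 82.5% power, as stated. The T2 figure of 81.0% also reproduces.

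**Step 2: chance of at least one false-positive squat result.** For k independent tests this is 1 − 0.95^k:

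- k = 2: 1 − 0.9025 = 9.8%
- k = 3: 1 − 0.8574 = 14.3%
- k = 4: 1 − 0.8145 = 18.5%

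For correlated tests, the value is the simulated share of equicorrelated normal draws in which any |Z| exceeds 1.96:

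| Squat tests counted | corr. 0 | corr. 0.5 | corr. 0.8 | corr. 0.9 |
|---|---|---|---|---|
| KFM at 3 and 6 months (2) | 9.8% | 9.0% | 7.8% | 7.1% |
| plus vGRF once (3) | 14.3% | 12.6% | 9.8% | 8.3% |
| plus vGRF twice (4) | 18.5% | 15.6% | 11.4% | 9.3% |

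Every cell exceeds 5%. The zero-correlation column is an upper reference, since repeated, related ratios on the same people are probably positively correlated.

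**Step 3: cost of control.** Holm over the two KFM tests compares the smaller p-value with 0.025 and, if that is significant, the larger with 0.05. With 15 per group the noncentrality is 1.369/√(2/15) = 3.75 on 28 degrees of freedom. Power is 95.1% at 0.05 and 90.9% at 0.025.

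The biofeedback SD of 0.183 matches the preliminary group of N=5 at 10 months. If 0.228 is used in both arms instead, the standardised difference is 0.283/0.228 = 1.241, and power at 15 per group is 90.7% at 0.05 and 84.2% at 0.025.

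**Step 4: why T2 should not share its alpha.** At 15 per group, T2 power is 81.0% at 0.05, 71.5% at 0.025 and 61.0% at 0.0125.

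**The case against.** The strongest reply is that the plan does name a primary outcome. T2 is one measure over one interval, powered at 15 per group; if it alone carries the confirmatory claim, that claim is tested at 5% and everything else is secondary. This stands to the extent that the T2 test needs no adjustment. It does not settle the squat claim, because the analysis section attaches the word efficacy to the squat ANCOVAs and gives T2 no special role.

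Two stronger readings are tempting, and the documents do not support either.

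- A reader might infer that efficacy can rest on any of a dozen or so tests, with an error rate of roughly 24% to 46%. The efficacy sentence does not cover strength or gait. The dynamometer procedure ("Select RTS Testing or RTS Testing plus 180 per sec depending on time point") lists measurements, not planned analyses, and strength is powered at 6 months only. No number of gait tests is given. The undefined strength mode and gait variables leave room for selective reporting, which is a separate matter from the error rate of the efficacy claim.
- A reader might infer that a significant squat result is probably false. The rates above are the chance of any rejection when no effect exists. They are not the probability that a given significant finding is wrong, and the small sample does not raise them.

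Two vGRF visits are also an inference, which is why three and four tests are both shown.

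**Conclusion.** The point holds for the squat tests. As written, the efficacy rule does not keep the false-positive chance at 5%: it is about 7% to 10% on the two KFM tests alone and about 8% to 18.5% on three or four squat tests. The position within each range depends on correlations that the documents do not give and on whether vGRF is tested once or twice. The excess over 5% does not depend on either.

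The conflict between T2 as primary and the squat ratios as the test of efficacy needs no assumption; it is on the page. Both defects should be corrected before the data are analysed. The T2 test itself is not inflated.

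**What to change.** In "Data analysis plan":

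1. State that the T2 change from 2 weeks to 6 months in the injured knee is the single primary test, two-sided at 0.05, in agreement with "Sample size analysis".
2. Base any claim of efficacy on squatting on the KFM impulse ILR only, with Holm at overall 0.05 across 3 and 6 months, and say that the claim is made for the visit or visits that pass.
3. State the visit or visits for the vGRF impulse ILR. Report it, with strength and gait, as secondary results that cannot support an efficacy claim by themselves. For vGRF there is a further reason: the interlimb ground reaction force is what the biofeedback screen displays as the target.

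**Cost.** SAP wording only, with no added participants or visits. T2 keeps its full 0.05 and its 81.0% power at 15 per group. KFM power at the strictest Holm step falls from 95.1% to 90.9% at 15 per arm on the plan's own inputs (84.2% if the larger SD applies to both arms), in either case above the 82.5% stated at 10 per group. The documents give no inputs for vGRF power, and under this fix none are needed.

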**Study Design**

1. Prospective, parallel clinical trial
2. Participants will be tested at enrollment (2 weeks after ACLR or when 50% weightbearing is allowed) and again after completing the study intervention at 3 months and 6 months post ACLR.

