**BEGINNING KINEMATIC SAMPLE RATE = 120 Hz**

1. Standing Calibration (named sc)
2. Self-selected walking speed (3, 6 months)
  - a. 8 trials collected on each limb (named walk01, etc.)
3. Bilateral squats (eyes open, arms folded across chest, re-do trial if balance is lost) (2 weeks & 3, 6 months)
  - a. 1 trial = 5 squats
  - b. 1 practice, 3 collected trials of max squats (named bilsquatmax01, etc.)
  - c. **Metronome: 3 seconds down, 3 seconds up**
    - i. **Verbal cues: “Down, 2, 3, Up, 2, 3”**
  - d. Pain is only to increase by 2/10 from pain in standing; either 1) modify depth of squats or foot position or 2) omit the testing (if unable to test involved max squats, still completed unininvolved max squats)

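### Squat, strength and gait are measured at 3 and 6 months but have no joint model, so a participant lost after 3 months adds nothing to the 6-month comparison; the effect is modest

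*Combined protocol and SAP*

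**What the plan says.** Under Study Design, participants are tested at enrolment and "again after completing the study intervention at 3 months and 6 months post ACLR". Within that schedule, squats are recorded at 2 weeks, 3 months and 6 months (Biomechanical Testing), and walking and quadriceps strength at 3 and 6 months only.

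The Data analysis plan then sets out these tests:

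- Squat KFM impulse interlimb ratio (ILR): "analyses of covariance (ANCOVA) will be used at 3 and 6 months after ACLR to test differences in the interlimb ratio", "after adjusting for baseline knee flexion moment impulse". Baseline is the only covariate named.
- Squat vGRF impulse ILR: "An ANCOVA will also be used to test differences in the ILR of the vertical ground reaction force impulse". No visit is named.
- T2, strength and gait: "Independent t-tests will be used to test the percent change in cartilage T2 relaxation time in the injured knee from 2 weeks to 6 months", with strength and gait listed in the same sentence. A time span is given for T2 only.

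Attrition appears only in the Sample size analysis: "To account for 10% attrition, 32 participants will be enrolled", later raised to 34 for the T2 and strength calculations. The inclusion rules in the Progression Plan and in the table of squat protocol modifications concern training sessions attended, not missed test visits. No repeated-measures model, imputation or missing-data rule is given.

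**The concern.** An ANCOVA or t-test of a 6-month outcome uses only participants who have a 6-month value. For squat, strength and gait, a participant lost between the visits has usually already supplied the same measurement at 3 months, and the planned tests cannot use it. The same holds in reverse for someone who misses 3 months and returns at 6.

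If loss after 3 months depends on how the knee was doing at 3 months, and does so differently in the two arms, the 6-month difference compares selected completers and is biased. That is possible here because the arms receive different feedback and cueing. Enrolling extra participants restores numbers but does not undo selection. If loss is unrelated to outcome, the cost is only some precision.

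The point covers missed follow-up visits. It does not cover a missing baseline or a test omitted for pain.

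**Working it through.** **Plan's own figures.** For the squat KFM ILR the pooled SD is √((0.183² + 0.228²)/2) = 0.2067. With 10 per group and a difference of 0.283, the noncentrality is 0.283/(0.2067 × √(2/10)) = 3.06 on 18 df, which gives two-sided power of 82.5%, as stated. Attrition: 28/0.9 = 31.1, rounded up to 32; 30/0.9 = 33.3, rounded up to 34. Both reproduce.

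**Assumptions not in the documents.** The 3-to-6-month correlation ρ is 0.5 to 0.7. For squats, the correlation r of baseline with each follow-up visit is 0.3 to 0.5. All 17 per arm are seen at 3 months, and the two biofeedback participants with the lowest 3-month values miss 6 months.

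**Bias, squat KFM ILR.**

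1. The two lowest of 17 standard normal values average −1.79 and −1.32. Removing them raises the mean of the other 15 by 3.11/15 = 0.207 SD. With the biofeedback SD this is 0.207 × 0.183 = 0.0379 on the 3-month scale.
2. The 6-month mean of completers moves by ρ times that amount. ANCOVA removes the part explained by baseline, about r². The bias is therefore about 0.0379 × (ρ − r²):

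| ρ | r | Bias | Share of 0.283 |
|---|---|---|---|
| 0.5 | 0.5 | 0.0379 × 0.25 = 0.009 | 3% |
| 0.5 | 0.3 | 0.0379 × 0.41 = 0.016 | 5% |
| 0.7 | 0.5 | 0.0379 × 0.45 = 0.017 | 6% |
| 0.7 | 0.3 | 0.0379 × 0.61 = 0.023 | 8% |

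3. Simulation of the same scenario gives 0.009 to 0.023 for the ANCOVA. An estimate using baseline and both visits stays within about 0.001 of the true difference.
4. If the two lowest are lost in both arms, simulated ANCOVA bias is no more than about 0.008 in size (3%). If about 12% are lost at random, or with the same dependence on the 3-month value in both arms, it is about zero. If the dependence runs in opposite directions by arm, it is −0.011 (ρ = 0.5) or −0.021 (ρ = 0.7).

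**Bias, strength and gait.** There is no baseline, so the shift is 0.207 × ρ × SD. For the quadriceps limb symmetry index (LSI): 0.207 × 0.5 × 21.1 = 2.2 points, or 3.1 points at ρ = 0.7, against a planned difference of 90.0 − 66.0 = 24.0. For gait KFM: 0.207 × 0.5 × 0.08 = 0.008, or 0.012 at ρ = 0.7, against 0.09. Each is 9-13% of the planned difference.

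**Precision.** Let m be the share of those seen at 3 months who are missing at 6. The relative variance of a 6-month arm mean is 1/(1−m) for completers and 1 + (m/(1−m))(1−ρ²) with both visits. Their ratio is 1 − mρ².

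- All 10% lost after 3 months: savings of 0.10 × 0.25 = 2.5% and 0.10 × 0.49 = 4.9%.
- Half lost earlier: m = 0.05/0.95 = 0.053, so 1.3% and 2.6%.
- For squats, baseline adjustment replaces ρ by the partial correlation (ρ − r²)/(1 − r²), which lowers the saving further. At ρ = r = 0.5 it is 0.25/0.75 = 0.33, a saving of 1.1%.

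**Power at 6 months,** with 17 per arm at 3 months, 15 at 6 months, and ρ of 0.5 to 0.7 (approximate, by t-test): squat ILR 95.1% rises to 95.7-96.2%; gait 84.5% to 85.6-86.7%; strength 85.2% to 86.3-87.4%. The plan states 91.8% for strength, which does not reproduce two-sided; that is a separate matter.

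**The case against.** The strongest reply is that baseline-adjusted ANCOVA at each visit is an accepted analysis for 34 participants, that it gives the same group differences as the joint model when no visit is missed, and that the biased scenario is an extreme: all loss in one arm, all after 3 months, and exactly the two lowest values. Nothing in the documents predicts this. Even then, the squat bias is 0.13 to 0.32 of a standard error (unadjusted standard error √(0.183²/15 + 0.228²/17) = 0.073). Squat ILR also has ample margin, since the plan needs 10 per arm and enrols 17. All of that stands, and it is why the point is modest.

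Several stronger readings are tempting, and the documents do not support them.

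- That the 6-month estimates are unbiased only if loss is random within each arm. ANCOVA also allows loss to depend on arm and baseline, and loss that is similar in both arms leaves the difference nearly unbiased.
- That the squat bias is 0.019 to 0.026 (7-9%). That is the result with r = 0, for raw means; the planned analysis adjusts for baseline.
- That the plan says participants are dropped. It is silent on missing data; exclusion is simply what these tests do by default.
- That every test is stated to be per visit. The visit is named only for the KFM ILR and T2.
- That the primary outcome is compromised. T2 is a single change from 2 weeks to 6 months and has no 3-month value to borrow.

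What does not stand is that the choice is pure preference. The joint model needs a weaker missingness assumption, and strength and gait have no baseline adjustment to limit the bias.

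**Conclusion.** The concern holds as an inexpensive improvement of modest size, limited to squat KFM ILR, squat vGRF ILR, quadriceps LSI and gait KFM. In the one-arm scenario the 6-month squat difference is off by about 0.01 to 0.02 (3-8% of 0.283), and the unadjusted strength and gait differences by somewhat more. Under random loss, or loss that is similar in both arms, bias is small or absent. The precision gain is at most about 2.5-5% of variance and smaller if some attrition precedes 3 months. All of these sizes rest on the assumed correlations and on the assumed timing and pattern of loss, none of which the documents give. The case rests mainly on protection against loss that differs by arm, and on settling the handling of missed visits in advance.

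**What to change.** In the Data analysis plan, for each of the four outcomes above, specify one repeated-measures model with group, visit and group-by-visit. For the two squat outcomes add the 2-week baseline and baseline-by-visit. Use an unstructured 2×2 covariance, REML and Kenward-Roger degrees of freedom. Include everyone with at least one of the two visits, and report the group difference at 3 and at 6 months. This also names the visits for vGRF, strength and gait.

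Keep the per-visit ANCOVA or t-test, with its nonparametric alternative, as a sensitivity analysis, so that the plan's clause on violated assumptions still has something to apply to. Leave the T2 analysis as it is.

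The cost is SAP wording and a few lines of code, with no new data or participants. The downside is that the model assumes missingness depends only on observed values, which should be stated, and that it needs a small-sample degrees-of-freedom method.
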